8.4.1.1. Time period and Frequency for collecting AE and SAE information

- AEs will be collected from the Screening visit (Visit 1), until the Exit Visit or EW (see [Section 8.4.1.3](#)), at the timepoints specified in the Time and Events Tables ([Section 8.1](#)).
- Medical occurrences that begin prior to the start of study treatment but after obtaining informed consent may be recorded on the Medical History/Current Medical Conditions section of the CRF.
- Any SAEs assessed **as related** to study participation (e.g., protocol-mandated procedures, invasive tests, or change in existing therapy) or related to a GSK concomitant medication will be recorded from the time a subject consents to participate in the study up to and including any Exit Visit or EW.
- All SAEs will be recorded and reported to GSK within 24 hours, as indicated in [Appendix 4](#).
- Investigators are not obligated to actively seek AEs or SAEs in former study subjects. However, if the investigator learns of any SAE, including a death, at any time after a subject has been discharged from the study, and he/she considers the event reasonably related to the study treatment or study participation, the investigator must promptly notify GSK.

NOTE: The method of recording, evaluating and assessing causality of AEs and SAEs plus procedures for completing and transmitting SAE reports to GSK are provided in [Appendix 4](#)

8.4.1.2. Method of Detecting AEs and SAEs

Care will be taken not to introduce bias when detecting AEs and/or SAEs. Open-ended and non-leading verbal questioning of the subject is the preferred method to inquire about AE occurrence. Appropriate questions include:

- “How are you feeling?”
- “Have you had any (other) medical problems since your last visit/contact?”

- “Have you taken any new medicines, other than those provided in this study, since your last visit/contact?”

8.4.1.3. Follow-up of AEs and SAEs

After the initial AE/SAE report, the investigator is required to proactively follow each subject at subsequent visits/contacts. All SAEs, and non-serious AEs of special interest (as related to the identified and potential risks described in [Table 3](#)) will be followed until resolution, until the condition stabilizes, until the event is otherwise explained, or until the subject is lost to follow-up (as defined in Section [6.7.4](#)). Further information on follow-up procedures is given in [Appendix 4](#).

8.4.1.4. Cardiovascular and Death Events

8.4.1.4.1. Cardiovascular Events

Cardiovascular-related AEs and SAEs that will require the investigator to complete event specific pages in the eCRF are listed in Section [13.4.3](#).

Cardiovascular events information should be recorded on the corresponding eCRF pages within one week of when the AE/SAE(s) are first reported. Please refer to [Appendix 4](#) for timelines for reporting AE/SAEs.

8.4.1.4.2. Death Events

In addition, all deaths will require completion of a specific death data collection page in the eCRF. The death data collection page in the eCRF includes questions regarding cardiovascular (including sudden cardiac death) and non-cardiovascular death.

Death information should be recorded on the death eCRF page within one week of when the death is first reported.

Please refer to [Appendix 4](#) for timelines for reporting SAEs.

8.4.1.5. Regulatory Reporting Requirements for SAEs

Prompt notification by the investigator to GSK of SAEs related to study treatment (even for non- interventional post-marketing studies) is essential so that legal obligations and ethical responsibilities towards the safety of subjects and the safety of a product under clinical investigation are met.

GSK has a legal responsibility to notify both the local regulatory authority and other regulatory agencies about the safety of a product under clinical investigation. GSK will comply with country specific regulatory requirements relating to safety reporting to the regulatory authority, Institutional Review Board (IRB)/Independent Ethics Committee (IEC) and investigators.

Investigator safety reports are prepared for suspected unexpected serious adverse reactions according to local regulatory requirements and GSK policy and are forwarded to investigators as necessary.

An investigator who receives an investigator safety report describing a SAE(s) or other specific safety information (e.g., summary or listing of SAEs) from GSK will file it with the IB and will notify the IRB/IEC, if appropriate according to local requirements.

8.4.2. Pregnancy

- Details of all pregnancies in female subjects will be collected after the start of dosing (Visit 1) until the Exit Visit or EW

Based on the absence of an identified reproductive hazard from preclinical studies, absence of a genotoxic potential, and very low levels of mepolizumab that might be present in semen, there is no recognized risk for mepolizumab to affect human sperm or the fetus if transferred to a female partner via semen. Therefore, the use of condoms or other methods of contraception in the male study subject is not required.

- If a pregnancy is reported then the investigator should inform GSK within 2 weeks of learning of the pregnancy and should follow the procedures outlined in [Appendix 5](#).

8.4.3. Physical Exams

- A complete physical examination will include, at a minimum, assessment of the Cardiovascular, Respiratory, Gastrointestinal and Neurological systems. Height and weight will also be measured and recorded in the eCRF.
- Investigators should pay special attention to clinical signs related to previous serious illnesses.

8.4.4. Vital Signs

- As detailed in the Time and Events Schedules ([Table 5](#), [Table 6](#), [Table 7](#) and [Table 8](#)) vital signs will be measured in a semi-supine position after 5 minutes rest and will include systolic and diastolic blood pressure and heart rate.
- Vital signs assessments will be taken **before** measurement of any clinic lung function tests or ECGs at the specified time point.

8.4.5. Electrocardiogram (ECG)

- Twelve-lead ECGs will be obtained at each time point specified in the Time and Events Schedules ([Table 5](#), [Table 6](#), [Table 7](#) and [Table 8](#)).
- ECG machines that automatically calculate the heart rate and measure PR, QRS, QT, and QTc intervals will be provided by GSK via a designated central laboratory.
 - The *same* QT correction formula *must* be used for *each individual subject* to determine eligibility for and discontinuation from the study. This formula may not be changed or substituted once the subject has been enrolled.
 - For example, as a subject is eligible for the study based on QTcF, then QTcF must be used for discontinuation of this individual subject as well.
 - Once the QT correction formula has been chosen for a subject's eligibility, the *same formula* must continue to be used for that subject *for all QTc data*

being collected for data analysis. Safety ECGs and other non-protocol specified ECGs are an exception.

- The QTc should be based on the average QTc value of triplicate ECGs. For example, if an ECG demonstrates a prolonged QT interval, obtain two more ECGs over a brief period, and then use the averaged QTc values of the three ECGs to determine whether the patient should be discontinued from the study.
- ECG measurements will be made after the subject has rested in the supine position for 5 minutes. The ECG should be obtained after the vital signs assessments but before lung function testing followed by other study procedures. Collection shortly after a meal or during sleep should be avoided since QT prolongation can occur at these times.
- Paper ECG traces will be recorded at a standard paper speed of 25mm/sec and gain of 10mm/mV, with a lead II rhythm strip. There will be electronic capture and storage of the data by a validated method.
- Paper ECG traces are required to be maintained at the site with other source documents.
- Refer to Section 6.5 and Section 6.6 for QTc withdrawal and discontinuation of IP criteria.

8.4.6. Clinical Safety Laboratory Assessments

All protocol required laboratory assessments (haematology and clinical chemistry) must be conducted in accordance with the Laboratory Manual, and Protocol Time and Events Schedule (Table 5, Table 6, Table 7 and Table 8). Laboratory requisition forms must be completed and samples must be clearly labelled with the subject number, protocol number, site/centre number, and visit date. Details for the preparation and shipment of samples will be provided by the laboratory and are detailed in the Laboratory Manual. Standard reference ranges for all safety parameters will be provided to the site by the laboratory responsible for the assessments.

All blood samples should be taken pre-dose, and will be sent to a central laboratory for analysis or for shipment to a GSK laboratory (details provided in the Laboratory Manual).

If additional non-protocol specified laboratory assessments are performed at the institution's local laboratory and result in a change in subject management or are considered clinically significant by the investigator (e.g., SAE or AE or dose modification) the results must be recorded in the eCRF. Please note that any non-protocol specified local laboratory result has the potential to break the blind due to the eosinophils result being available. Please see the Study Reference Manual for guidance.

Refer to the Laboratory Manual for appropriate processing and handling of samples to avoid duplicate and/or additional blood draws.

Haematology, clinical chemistry and additional parameters to be tested are listed in [Table 9](#).

Table 9 Protocol Required Safety Laboratory Assessments

Laboratory Assessments	Parameters			
Haematology	Platelet Count		RBC Indices:	WBC count with Differential:
	RBC Count		MCV	Neutrophils
	Hemoglobin		MCH	Lymphocytes
	Hematocrit			Monocytes
				Eosinophils
				Basophils
Clinical Chemistry ¹	BUN	Potassium	AST (SGOT)	Total and direct bilirubin
	Creatinine	Sodium	ALT (SGPT)	Total Protein
	Glucose	Calcium	Alkaline phosphatase	Albumin
Other Screening Tests	
 • Hepatitis B (HBsAg) • Hepatitis C (Hep C antibody)² • FSH and estradiol (if clinically indicated, in women of non-child bearing potential only) • Alcohol and drug screen (if clinically indicated, to include at minimum: amphetamines, barbiturates, cocaine, opiates, cannabinoids and benzodiazepines) • Urine hCG Pregnancy test (for women of child bearing potential)³ 			

NOTES :
 
 1. Details of Liver Chemistry Stopping Criteria and Required Actions and Follow-Up Assessments after liver stopping or monitoring event are given in Appendix 2 and Appendix 3 2. If Hepatitis C antibody positive result, a hepatitis C confirmatory test should be automatically performed to confirm the result. Test should be repeated as necessary if clinically indicated. 3. Local urine testing will be standard for the protocol unless serum testing is required by local regulation or ethics committee. 				

All laboratory tests with values that are considered clinically significantly abnormal during participation in the study should be repeated until the values return to normal or baseline. If such values do not return to normal within a period judged reasonable by the investigator, the etiology should be identified and the sponsor notified.

To maintain the treatment blind, the site and the central study team will not be sent information on haematology differential or IL-5 value from any visits post-randomization.

8.4.6.1. Immunogenicity

Blood samples will be collected for the determination of anti-mepolizumab antibodies, prior to dosing, as detailed in the Time and Events Schedules ([Table 5](#), [Table 7](#) and [Table 8](#)).

Details for sample collection and processing may be found in the SRM.

8.5. Biomarker(s)/Pharmacodynamic Markers

The following tests will be performed on the blood sample:

Blood eosinophil counts will be recorded as part of the standard haematological assessments performed at the visits specified in the Time and Events Schedules ([Table 5](#), [Table 6](#), [Table 7](#) and [Table 8](#)). The site staff and central study team will be blinded to each subject's eosinophil count (including blood count differential) from any visits post-randomization.

Blood (serum) samples will be collected during this study and may be used for the purposes of measuring biomarkers to identify factors that may influence the development of asthma and/or medically related conditions, as well as the biological and clinical responses to mepolizumab. Blood samples for biomarker testing will be stored for up to 15 years. Those biomarker results, which have the potential to break the blind will be blinded to the site staff until the clinical study report is finalised.

Full details regarding sample collection, processing and shipping are provided in the central Laboratory Manual.

8.6. Genetics

Data and genetic samples have previously been obtained from precursor studies: MEA112997, MEA115588, and MEA115575. These samples may be used as part of a genetic analysis using data collected in this study, if relevant. No additional genetic samples are required.

9. DATA MANAGEMENT

- For this study subject data will be entered into GSK defined CRFs, transmitted electronically to GSK or designee and combined with data provided from other sources in a validated data system.
- Management of clinical data will be performed in accordance with applicable GSK standards and data cleaning procedures to ensure the integrity of the data, e.g., removing errors and inconsistencies in the data.

- Adverse events and concomitant medications terms will be coded using MedDRA (Medical Dictionary for Regulatory Activities) and an internal validated medication dictionary, GSKDrug.
- CRFs (including queries and audit trails) will be retained by GSK, and copies will be sent to the investigator to maintain as the investigator copy. Subject initials, date of birth or other personally identifiable information will not be collected or transmitted to GSK according to GSK policy.

10. STATISTICAL CONSIDERATIONS AND DATA ANALYSES

10.1. Hypotheses

The study is designed to test the superiority of continued mepolizumab 100 mg SC treatment vs. mepolizumab discontinuation (placebo). Significance tests will be performed at the two-sided 5% alpha level (one-sided 2.5%).

10.2. Sample Size Considerations

Sample size is based on the primary efficacy endpoint of time to first clinically significant exacerbation.

10.2.1. Sample Size Assumptions

With a sample size of 300 randomised subjects (150 per arm), it is estimated that statistical significance will be declared if the proportion of subjects with a clinically significant exacerbation following withdrawal of mepolizumab is 52.5% compared to 40% for those continuing to receive mepolizumab (hazard ratio = 0.686).

If the true hazard ratio is 0.55 (corresponding to a proportion with an exacerbation following discontinuation of mepolizumab of 60.5%), then the study has a probability of 90% of observing a hazard ratio of < 0.686 and therefore the study has 90% power for declaring statistical significance on this endpoint.

The estimated event rate for subjects randomized to mepolizumab is based on interim data from study MEA115666 which suggests 40% of subjects will experience an exacerbation within one year of randomization. In study MEA115588, the observed hazard ratio for the combined treatment arms of mepolizumab 100mg SC and 75mg SC vs placebo was 0.5. A lower event rate among those discontinuing mepolizumab is expected in this study than was observed for placebo in MEA115588 because of the continuing effects of previous treatment with mepolizumab. The sample size calculations assume 20% of subjects will withdraw prior to the end of the double-blind treatment phase before experiencing an exacerbation.

10.2.2. Sample Size Sensitivity

If the true hazard ratio or proportion of events seen within the mepolizumab discontinuation (placebo) treatment group observed within this study differs from the

values assumed within Section 10.2.1, the power to detect a difference between the two treatment groups will be affected.

Table 10 illustrates the estimated power which would be obtained with different hazard ratios and proportion of events observed within the mepolizumab discontinuation (placebo) group, assuming a sample size of 150 randomised subjects per arm.

Table 10 Effect on power for varying hazard ratios and proportions of events observed within the mepolizumab discontinuation (placebo) treatment group

Proportion of events within the placebo group	Hazard ratio						
	0.40	0.45	0.50	0.55	0.60	0.65	0.70
50%	98.6%	96.0%	90.9%	82.6%	71.3%	58.0%	44.3%
55%	99.2%	97.5%	93.6%	86.4%	75.8%	62.5%	48.1%
60%	99.6%	98.5%	95.5%	89.5%	79.8%	66.7%	51.8%
65%	99.8%	99.1%	97.0%	92.1%	83.3%	70.6%	55.5%

10.2.3. Sample Size Re-estimation or Adjustment

No sample size re-estimation is planned for this study.

10.3. Data Analysis Considerations

10.3.1. Analysis Populations

All Subjects Enrolled (ASE) Population

The ASE population will comprise all subjects enrolled and for whom a record exists on the study database. This population will be used for summarising reasons for screen and run-in failures and to report data collected within the variable open-label run-in (Part A) and fixed run-in (Part B).

Intent-to-Treat (ITT) Population

This population will consist of all randomized subjects who receive at least one dose of double-blind study medication, and will be the primary population for all analyses of efficacy and safety data. In cases where there is a discrepancy between the treatment to which a subject was randomized and the treatment they actually received a profile of the subjects' data will be produced.

Per Protocol (PP) Population

The PP population will consist of all subjects in the ITT population who have not been identified as full protocol deviators with respect to criteria that are considered to impact the primary efficacy analysis. The decision to exclude a subject from the PP Population or exclude part of their data from the PP Population analyses will be made prior to breaking the blind. The PP population will be used for a supplementary analysis of the primary endpoint.

10.3.2. Interim Analysis

No interim analysis of data is planned for this study.

10.4. Key Elements of Analysis Plan

Full details of all analysis methods to be used will be provided in the RAP which will be finalised prior to unblinding.

The study will be unblinded once the final subject has completed the Exit or EW Visit, all queries for data collected up to this time are resolved and the clinical study database is frozen.

10.4.1. Primary Analyses

Time to first clinically significant exacerbation will be compared between treatment groups using a Cox's proportional hazards model allowing for covariates of region, exacerbations in the year prior to randomization and use of baseline maintenance oral corticosteroids (OCS vs no OCS). For geographical region, a grouping system for countries will be defined in the RAP.

Only Part C exacerbation data will be included in the primary analysis from the start of double-blind treatment until no greater than 4 weeks post-last-dose of double-blind treatment. The analysis will be performed on the Intent-to-Treat (ITT) population. A supporting analysis of the PP population will also be performed.

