Vital Signs	X	X	X	X	X	X	X	X	X	X	X	X	X	X	X	X	X	X	X
12-lead ECG	X		X							X								X	X
Adverse Events	X	X	X	X	X	X	X	X	X	X	X	X	X	X	X	X	X	X	X
Laboratory Assessments²																			
Haematology	X		X	X	X	X	X	X	X	X	X	X	X	X	X	X	X	X	X
Chemistry (incl. LFT)	X		X	X						X								X	X
Biomarkers				X	X	X	X	X	X	X								X	X
Pregnancy Test ³	U	U	U	U	U	U	U	U	U	U	U	U	U	U	U	U	U	U	U
Immunogenicity			X															X	X
Efficacy Assessments²																			
Subject/Clinician Global Impression Rating				X			X			X			X					X	X
Subject/Clinician Rating of Response to Therapy							X			X			X					X	X

PARTS B&C Procedures	Fixed Run-in Part B		EW from Part B ⁷	Randomization	Double-Blind Treatment Part C (window is ± 1 week)													IPDISC/EW Visit ⁷		
	Visit	B1			B2 ¹	Part B EW	C1	C2	C3	C4	C5	C6	C7	C8	C9	C10	C11		C12	C13
Week of Study	-4 ± 1	-4 \pm 1 ¹		0	4	8	12	16	20	24	28	32	36	40	44	48	52			
Collect/review paper diary	X	X	X	X	X	X	X	X	X	X	X	X	X	X	X	X	X	X	X	
Contact IRT			X	X														X	X	
Complete eCRF	X	X	X	X	X	X	X	X	X	X	X	X	X	X	X	X	X	X	X	X

1. Visit B2 is only intended for subjects who experience an exacerbation in the run-in Part B which is not resolved within 7 days of Visit C1 or subjects who fail eDiary Compliance Criteria (Section 6.3).
2. All assessments to be completed prior to dosing.
3. Urine pregnancy tests (U) should be conducted every 4 weeks for women of child bearing potential.
4. Subjects eDiary entries should be reviewed by the site weekly during Part C
5. An unblinding card will be dispensed after Randomization at Visit C1.
6. The eDiary is only collected at an Early Withdrawal visit and not at IPDISC in Part C.
7. IPDISC/EW visit should be conducted 4 ± 1 weeks from the subject's last dose
8. Only *pre*-bronchodilator spirometry required at this visit.

Table 8 Time and Events Table: Optional Open-Label Switch to Mepolizumab – Part D

PART D Procedures	OPTIONAL Open-Label Switch to mepolizumab Part D ¹ (window is \pm 1 week)														IPDISC/EW Visit ⁸
	Visit	D1	D2	D3	D4	D5	D6	D7	D8	D9	D10	D11	D12	D13	
Week of Study²	0	4	8	12	16	20	24	28	32	36	40	44	48	52	
Safety Assessments³															
Concomitant Medication	X	X	X	X	X	X	X	X	X	X	X	X	X	X	X
Physical Examination														X	X
Vital Signs	X	X	X	X	X	X	X	X	X	X	X	X	X	X	X
12-lead ECG							X							X	X
Adverse Events	X	X	X	X	X	X	X	X	X	X	X	X	X	X	X
Laboratory Assessments³															
Haematology ⁴				X			X			X				X	X
Chemistry (incl. LFT)							X							X	X

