## 2. SUMMARY OF KEY PROTOCOL INFORMATION

### 2.1. Changes to the Protocol Defined Statistical Analysis Plan

This RAP is based on the protocol amendment 02 (Dated: 07-Jul-2016) of study 201810 (GSK Document No: [2015N232375\\_03](#)) and eCRF Version 1.0.

There were no changes or deviations to the originally planned statistical analysis specified in protocol amendment 02 (Dated: 07-Jul-2016).

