#### 7.1.4. Strategy for Intercurrent (Post-Randomization) Events

A hypothetical estimand strategy will be applied in the handling of the intercurrent event of discontinuation of double-blind treatment. The treatment effect therefore refers to the outcome if all patients had continued to take double-blind treatment.

Only the On-treatment (Part C) period will be used in the analysis and subjects will be analysed according to the treatment each subject received for more than 50% of injections within Part C (see Section 5.1).

All subjects will be considered to be at risk from their first dose of double-blind treatment at visit C1. Subjects who complete Part C will be considered to be at risk up to their Week 52 (Exit Visit/C14) visit date. Subjects who discontinued double-blind treatment prior to experiencing an exacerbation (event) will be censored at the time of treatment discontinuation [see On-treatment (Part C) definition within Section 11.4.2].

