**11.4.2. Treatment Phases (Exacerbations and Healthcare Resource Use)**

Exacerbations and healthcare resource use will be classified into treatment phases according to the time of occurrence/assessment relative to the dates of the study treatment and/or the participation of subjects within specific study parts (as dictated by attendance at specific visits) as shown in the table below:

Treatment Phase	Definition
Pre-treatment	Onset Date & time < First dose of open-label mepolizumab
On-treatment (Parts A/B)	Subjects who are randomized and receive double-blind treatment: First dose of open-label mepolizumab ≤ Onset Date & time < First dose of double-blind treatment Subjects who are not randomized: First dose of open-label mepolizumab ≤ Onset Date & time ≤ Earliest of (1) Last dose of open-label mepolizumab + 28 days or (2) Early Withdrawal visit date 
Post-treatment (Parts A/B)	Subjects who are not randomized: Onset Date & time > Earliest of (1) Last dose of open-label mepolizumab + 28 days or (2) Early Withdrawal visit date 
On-treatment (Part C)	Subjects completing study Part C: First dose of double-blind treatment ≤ Onset Date & time ≤ C14 (Exit Visit) visit date Subjects discontinuing study treatment/withdrawing early from within Part C: First dose of double-blind treatment ≤ Onset Date & time ≤ Earliest of (1) Last dose of double-blind treatment + 28 days or (2) Early Withdrawal / IP Discontinuation visit date Subjects who switch to study Part D: First dose of double-blind treatment ≤ Onset Date & time < First dose of open-label mepolizumab within Part D
Post-treatment (Part C)	Subjects completing study Part C: Onset Date & time > C14 (Exit Visit) visit date Subjects discontinuing study treatment/withdrawing early from within Part C: Onset Date & time > Earliest of (1) Last dose of double-blind treatment + 28 days or (2) Early Withdrawal / IP Discontinuation visit date
On-treatment (Part D)	Subjects completing study Part D: First dose of open-label mepolizumab within Part D ≤ Onset Date & time ≤ D14 (Exit Visit) visit date Subjects discontinuing study treatment/withdrawing early from within Part D: First dose of open-label mepolizumab within Part D ≤ Onset Date & time ≤ Earliest of (1) Last dose of open-label mepolizumab within Part D + 28 days or (2) Early Withdrawal / IP Discontinuation visit date

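### Protocol 10.4.1 ends the primary risk period 4 weeks after the last double-blind dose for everyone; the SAP runs switchers to the first Part D dose and completers to the Exit Visit, and SAP 2.1 declares no change

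*Protocol*

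**What the plan says.** Protocol 10.4.1 restricts the primary analysis to Part C exacerbations, "included in the primary analysis from the start of double-blind treatment until no greater than 4 weeks post-last-dose of double-blind treatment". It makes no distinction between completers, switchers and other discontinuations. Protocol 10.4.2 does run completers to the Exit Visit, but only for secondary and other endpoints. For switchers and early stoppers it keeps a limit of roughly 4 weeks.

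The SAP sets the primary risk period by disposition:

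- **Completers** (7.1.4): "Subjects who complete Part C will be considered to be at risk up to their Week 52 (Exit Visit/C14) visit date".
- **Switchers** (11.4.2): "First dose of double-blind treatment ≤ Onset Date & time < First dose of open-label mepolizumab within Part D", with no 28-day limit.
- **Subjects who discontinue or withdraw without switching** (11.4.2): the earlier of last dose plus 28 days and the Early Withdrawal or IP Discontinuation visit date.

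SAP 2.1 states: "There were no changes or deviations to the originally planned statistical analysis specified in protocol amendment 02". On visit timing, the footnote to protocol Table 7 says "IPDISC/EW visit should be conducted 4 ± 1 weeks from the subject's last dose", and Part C clinic visits carry a window of one week either side. Under protocol 5.1 the IP Discontinuation visit and the first Part D visit are held on the same day.

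**The concern.** The two documents define different risk periods for the primary endpoint, and the SAP does not record the difference. If every visit fell exactly 28 days after the last, the rules would agree. With a one-week window, a permitted dosing interval can exceed 28 days, and the rules then select different events.

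The protocol rule also has a defect of its own: the outcome helps to decide which dose is the last one. Take two subjects dosed on day 0 whose next visit falls on day 33. One has a first exacerbation on day 31 and switches on day 33. Day 0 was that subject's last double-blind dose, so the subject is censored at day 28 and the event is lost. The other is event-free and is dosed on day 33, so days 29 to 33 count as risk time. Events are removed from a stretch of time that stays in the denominator for everyone else.

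At stake are a few primary events and some power. There is also the question of which result is the pre-specified one if the p-value lies close to 0.05.

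**Working it through.** **The plan's own figures first.** Protocol 10.2.1 gives 150 per arm, 40% and 60.5% with an event, a true hazard ratio of 0.55, 20% withdrawing before an event, and 90% power. Protocol 10.1 gives two-sided 5% alpha.

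- Hazard ratio from the proportions: ln(0.60)/ln(0.395) = 0.550.
- Events: 0.8 × 150 × (0.40 + 0.605) = 120.6. Protocol 5.3 expects about 120.
- Schoenfeld power: Φ(√120.6/2 × |ln 0.55| − 1.96) = Φ(1.32) = 90.7%, against 90% stated.

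**Where the two rules differ.**

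| First exacerbation starts more than 28 days after the latest dose, and the subject then | Protocol 10.4.1 | SAP 11.4.2 |
|---|---|---|
| takes a further double-blind dose | counted | counted |
| switches to Part D at the next visit | not counted | counted |
| stops without switching | not counted | not counted |
| has had the Week 48 dose and attends the Exit Visit | not counted | counted |

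Only the second and fourth rows separate the documents.

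**Switchers.** Affected events ≈ 120.6 × (share who switch at the next visit) × (mean days beyond 28 ÷ mean interval). Neither factor is in the documents, so both are assumptions.

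For the full window, let both visits that bound an interval be uniform over ±7 days. The interval minus 28 is then triangular on −14 to 14.

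- Mean excess over 28 days: 14/6 = 2.33 days, or 2.33/28 = 8.3%. This allows intervals of up to 42 days, whereas the switch visit is due within 35 days of the last dose.
- Holding longer intervals at 35 days removes 7³/(6 × 196) = 0.29 day. That leaves 2.04 days over a mean interval of 27.71, or 7.4%. Events: 120.6 × 0.074 = 8.9.
- Excluding intervals over 35 days instead leaves 1.33 days over a mean interval of 26.67, or 5.0%. Events: 6.0.

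| Mean days beyond 28 | 25% switch | 50% switch | All switch |
|---|---|---|---|
| 0 (exact visits) | 0 | 0 | 0 |
| 0.25 | 0.3 | 0.5 | 1.1 |
| 0.5 | 0.5 | 1.1 | 2.2 |
| 1 | 1.1 | 2.2 | 4.3 |
| 2.04 (full window, intervals held at 35 days) | 2.2 | 4.4 | 8.9 |

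**Completers.** Event-free completers number 0.8 × 150 × 0.60 = 72 on mepolizumab and 0.8 × 150 × 0.395 = 47.4 on placebo. With constant hazards over 364 days, they would have 72 × 0.00140 + 47.4 × 0.00255 = 0.222 events per day. At a mean excess of 2.33 days this is 0.5 event. It reaches 1.6 only if every Exit Visit is 7 days late (0.222 × 7). The switcher formula applies the excess to all 120.6 events, including those in the last interval, so the two figures should not simply be added.

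**Power.** Losing 8.9 events leaves 111.7: Φ(√111.7/2 × 0.598 − 1.96) = Φ(1.20) = 88.5%, a fall of 2.2 points. Losing 2 events gives 90.2%.

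**The case against.** The strongest reply is that protocol 10.4 leaves full analysis detail to the RAP, finalised before unblinding, and the RAP already uses the better rule. On that view no switch-triggering exacerbation will be lost in the planned analysis, and what is missing is one entry in SAP 2.1. Much of this stands. The loss described above follows from reading 10.4.1 literally, and the SAP suggests that this is not what will be run. But detail in a RAP can fill a gap. It cannot pass an explicit upper limit in the protocol while stating that nothing changed.

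A second reply is that the size is speculative. That is right as far as it goes. Part D is optional and at the investigator's discretion. Protocol 5.3 says about 120 subjects will meet the switch criteria, not that they will switch. Its totals (120 events, 120 completers and 60 withdrawals making 300) fit near-universal switching but do not establish it.

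A reader might infer a fixed number of affected events, with a floor of two or so and ten within reach. The documents support neither end. The number is zero with exact visits and under one in several plausible settings. About ten requires switch visits later than the 35 days that the Table 7 footnote allows. A reader might also infer a shifted hazard ratio. That would need exacerbators in the two arms to switch at different rates or at different delays, and neither document gives a basis for such a split. With equal rates and delays, the same fraction of events is lost in each arm and the main effect is on power.

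**Conclusion.** The conflict is real, concerns the risk period of the primary endpoint and is undeclared. The protocol's cap, taken literally, is also the worse rule, because it drops switch-triggering events while counting the same days as risk time for event-free subjects.

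The size is modest: from 0 to about 9 of roughly 120 events, with a power loss of about 2 points at most. The upper end assumes that every exacerbator switches at the next visit, that visits spread uniformly over the full window, and that switch visits fall no later than 35 days after the last dose. Completers matter very little.

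The documents do not support saying that the planned analysis will lose these events or that the hazard ratio will be biased. They do support saying that the pre-specified rule is ambiguous and should be settled before unblinding.

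**What to change.** Before unblinding:

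1. In SAP 2.1, list the SAP cut-off as a change from protocol 10.4.1 and name it as the primary rule. Align 10.4.1 if the protocol is being amended anyway. An amendment for this alone would need ethics review (protocol 11.2) and is not necessary.
2. Remove the same defect for subjects who stop without switching, since the SAP still drops an event of theirs that starts after day 28. One way is to end their risk period at the IP Discontinuation visit date rather than at the earlier of that date and day 28. Apply this to all such subjects, with or without an event, so that the rule does not depend on the outcome. The 28-day limit can stay where no such visit is held.
3. Add one sensitivity analysis of the primary endpoint under the protocol's 4-week cap, and report by arm how many primary events began more than 28 days after the last double-blind dose.

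The cost is one SAP entry, one edited definition, one extra Cox model and one count. The analysis will also include a few days of risk time beyond 28 days after the last dose. Treatment, visits and data collection are unchanged.
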